Furthermore, I hereby confirm that I will have and will use the availability of adequate resources, personnel and facilities for the conduct of this trial.

Principal Investigator's Name:
Principal Investigator's Title:
Principal Investigator's Address:
Principal Investigator's Signature:
Date of signature:

Version: **2.0**; **08** Sep **2021** Page **12** of **61**

Abbreviation	Definition
AsIgE	Allergen Specific IgE
AR	Allergic Rhinitis
AUC	Area Under the Curve
AE	Adverse Event
BoV	Bag-on-Valve
CA	Competent Authority
CIP	Clinical Investigation Plan
CRF	Case Report Form
EC	Ethic Committee
GDPR	General Data Protection Regulation
IFU	Instruction For Use
IgE	Immunoglobulin E
MDR	Medical Device Regulation
PI	Principal Investigator
PNF	Primary Notification Form
RAST	RadioAllergoSorbant Test
SAP	Statistical Analysis Plan
WURSS-K	Wisconsin Upper Respiratory Symptom Survey for kids

Version: **2.0**; **08** Sep **2021**Study Number: **LPH-2101**Page **13** of **61**

2. Synopsis

Sponsor:	LALLEMAND PHARMA AG
Coordinating/Principal	Pr [name], University Children Hospital, Lublin, Poland
Investigator	
Short Title:	SYMBIOFILM-TAK
CIP version:	Version 2.0 – 08 Sep 2021
Competent Authority:	N/A
Rational	Healsea® Children is a seawater-based nasal spray supplemented with a natural Symbiofilm® extract (0.02%) isolated from marine bacteria. Symbiofilm® is an exopolymeric composition with emulsifying properties, in vitro antibiofilm activity and detachment properties against various bacterial pathogens involved in respiratory tract infections. Symbiofilm® has no bacteriostatic nor bactericidal activities. Healsea® Children is indicated in the cleaning and moistening of nasal mucosa during common cold and rhinitis. The common cold is an acute viral infection of the upper respiratory tract,
	involving, to variable degrees, sneezing, nasal congestion and discharge (rhinorrhea), sore throat, cough, low-grade fever, headache, and malaise. It can be caused by members of several families of viruses; the most common are the more than 100 serotypes of rhinoviruses. Acute viral rhinitis is generally self-limiting. In children where the illness is not self-limiting and extends beyond 7-10 days, many agree that a bacterial infection is likely. Bacterial over infections and progression to a chronic state are favoured by the formation of biofilms, which facilitate bacterial growth and persistence as well as reducing antibiotic efficacy.
	Allergic diseases may play a particular role in promoting the respiratory infection recurrences. The physiological immune response is impaired in allergic subjects and allergic inflammation favours predisposition to respiratory infections. Subjects with allergic disorders may have functional defect of type 1 immune response that is relevant in fighting infections. Allergic rhinitis (AR) may affect up to 40% of the paediatric population. Nasal symptoms are caused by exposure to an allergen to which a patient is sensitized. Typical allergens include house dust mite, grass pollen, tree pollen, weed pollens, cat, dog and moulds. Allergic rhinitis can thus be seasonal or perennial, according to the relevant allergen. AR is characterized by typical nasal symptoms and IgE-mediated inflammation. The allergic inflammatory process releases many cytokines and other proinflammatory proteins. Inflammation caused by nasal allergy leads to obstruction, fluid accumulation and acute disease. If these diseases are unsuccessfully treated, a chronic state of inflammation, obstruction, and infection develops that can cause mucosal damage and, ultimately, chronic disease. For these reasons, the paediatric IgE-dependent allergic population that is more prone to common cold represents a suitable target for Healsea® Children.

Version: **2.0**; **08** Sep **2021**Study Number: **LPH-2101**Page **14** of **61**

During this prospective observational study, one cohort of IgE-dependent allergic children with early symptoms of infectious rhinitis will be followed, children being treated with Healsea® Children on top of common cold conventional therapies or with conventional therapies only (excluded nasal irrigation).

Conventional therapies for non-complicated infectious rhinitis are symptomatic but are not without side effects. For example, decongestant use can increase blood pressure, antihistamine intake is associated with drowsiness.

Healsea® Children represents an interesting alternative that can not only improve acute infectious rhinitis symptomatology but could also limit the complication and progression to chronic state.

This observational study aimed to confirm the benefit of Healsea® Children in a real life setting in children with perennial allergy.

Objectives

Primary Objective:

- To assess the impact of both treatment modalities (Healsea® Children on top of common cold conventional therapies and common cold conventional therapies only) to reduce acute infectious rhinitis symptoms in 6-10 years old allergic children during a 10-day treatment period.

Secondary Objectives:

- To assess the impact of both treatment modalities to reduce the duration of each infectious rhinitis symptom as rated by the Wisconsin Upper Respiratory Symptom Survey for kids (WURSS-K).
- To assess the impact of both treatment modalities to reduce complications of the acute phase during a 20-day follow-up phase.
- To assess the impact of both treatment modalities on the intake of conventional common cold medication (antibiotics, antipyretics, mucolytics, decongestants, antitussives, systemic and topical corticosteroids).
- To assess the impact of both treatment modalities to reduce the person to person spreading among close contacts (parents, siblings).
- **Safety**: to assess systemic and local tolerance of **Healsea® Children** over the study period.

Endpoints:

Primary Endpoint:

The primary endpoint is the AUC of the WURSS-K during first 10 days of symptoms.

The WURSS-K will be assessed once daily in the evening, considering the symptoms from the morning to the evening, during D1-D10.

Secondary Endpoints:

- Duration of cold symptoms (items 2 to 7) will be assessed by means of the WURSS-K (assessed once daily in the evening).

During treatment period, the WURSS-K will be assessed once daily in the evening, taking into account the symptoms from the morning to the evening.

Version: **2.0**; **08** Sep **2021** Page **15** of **61** Study Number: **LPH-2101**

After D10, the WURSS-K will be assessed once daily until the subject feels not
sick for two consecutive days.

For each item, the duration is defined as the number of symptomatic days between D1 and the first day the subject reports not having the symptom for two consecutive days.

To be noticed that the duration may be censored at day 30.

- Number of subjects who develop respiratory complication requiring antibiotic prescription during a 20-day follow-up period.
- Frequency and number of days of use of concomitant treatments that may affect common cold symptoms (antibiotics, antipyretics, systemic or local mucolytics, decongestants, antitussives, systemic and topical corticosteroids).
- Number of family members in close contact developing common cold symptoms after the patient all over the study period.
- **Safety**: Assessment of adverse event/incidents/ undesirable expected side effects throughout the study.

Indication:

Treatment of acute rhinitis in children 6-10 years old

Investigation Design:

Prospective, open label, observational study

Visit 1 (V1) – (Day 1): Screening/Inclusion

Information and provision of the information sheet to legal guardians and participants, consent and assent signatures, demographic data and medical history, ongoing medication, physical and clinical examination, inclusion/non-inclusion criteria, record of patient choice regarding Healsea® Children use.

D1-D10 (at home):

Daily completion of the electronic diary (WURSS-K, adverse events/incident/undesirable expected side effects and concomitant medications, contamination of relatives if applicable, Healsea® Children daily administration if applicable).

D5±2 (at home): Telephone call 1

Investigator/nurse call to review patient status and study progress, adverse event/incident/undesirable expected side effects and concomitant treatments.

Visit 2 (V2) – (Day 10±2): End of treatment

End of Healsea® Children nasal spray treatment if applicable, assessment of symptoms, diary review, reporting of adverse events/incident/undesirable expected side effects.

D11-D30±5 (at home):

Daily completion of the diary (Adverse event, concomitant medications, contamination of relatives if applicable, WURSS-K if applicable, until the subject feels not sick for two consecutive days).

D20±2 (at home): Telephone call 2

Investigator/nurse call to review patient status and study progress, adverse events and concomitant treatments.

Version: **2.0**; **08** Sep **2021** Page **16** of **61** Study Number: **LPH-2101**

	Visit 3 (V3) – (Day 30±2): End of study					
	Physical and clinical examination, diary review, reporting of adverse events and					
	concomitant treatments.					
Number of Subjects:	15 centers will be involved in this study. We plan to follow a cohort of 200					
	subjects . The recruitment will be competitive in both group, exposed to					
	Healsea® Children or not exposed to Healsea® Children. However, when 100					
	patients will be recruited in one group, the recruitment will be stopped in this					
Towart Downlotions	group but will continue in the other group until 100 patients to be enrolled.					
Target Population:	Children with allergic rhinitis and symptoms of acute infectious rhinitis					
Inclusion/Exclusion criteria:	Inclusion Criteria:					
criteria.	Subjects will be enrolled if they meet all of the following criteria:					
	1. Male/Female subjects ≥6 and ≤10-year-old					
	 AsIgE ≥ class 2 (RAST) or positive prick test for at least one perennial allergen 					
	3. Acute infectious rhinitis/rhinosinusitis for ≤48h before trial entry					
	 Patient presenting with fever ≥ 37.5 °C at screening 					
	5. Symptoms of headache, muscle ache, chilliness, sore throat, blocked					
	nose, runny nose, cough, sneezing with a total score ≤9 (according to					
	a physician-rated symptom score; scale: $0 \rightarrow 3$ [0: no symptom to 3:					
	severe intensity])					
	6. At least one of these symptoms: sore throat, runny nose or blocked					
	nose (i.e., with a score ≥1)					
	7. Written consent obtained from parent/legal guardians					
	8. Written assent obtained from patient					
	Non-inclusion Criteria:					
	Subjects will not be enrolled if one of the following criteria is present:					
	Known hypersensitivity/allergy to any component of the test device					
	Medical history that is considered by the investigator as a reason for non-inclusion,					
	Severe nasal septum deviation or other condition that could cause					
	nasal obstruction such as the presence of nasal polyps					
	4. History of nasal or sinus surgery that in the opinion of the investigator					
	may influence symptom scores					
	5. Antibiotic intake within 2 weeks before screening					
	Systemic corticosteroids within 4 weeks before screening					
	7. Antihistamines intake for allergy when treatment was started from less					
	than 4 weeks					
	8. Bacterial lysate intake within 6 months before screening					
	9. Chronic decongestant use					
	5. Chrome decongestant asc					

Version: **2.0**; **08** Sep **2021** Page **17** of **61**

	10. Recent (within the previous 2 days) intake of a common cold medicine			
	that in the opinion of the investigator may influence symptom score at			
	screening (NSAID, nasal decongestants, cough medicines)			
Number of sites:	15 sites in Poland			
Treatments:	-Healsea® Children nasal spray, one puff (1-2 sec) in each nostril twice a day for			
	10 days on top of conventional therapies as needed			
	or			
	-Conventional therapies only, nasal irrigation excluded			
Comparator Device:	Non applicable			
Duration of	Duration of inclusion period: 3 months			
investigation:	Duration of patient's participation: 30 days			
_	Total study duration: 4 months			
Study Start Date:	September 2021			
Statistical Analysis:	The cohort is described: continuous variables will be summarized using the			
,	mean, standard deviation, median, minimum, maximum and quartiles,			
	categorical variables will be summarized using frequency counts and			
	percentages.			
	Two groups (called treatment groups for a sake of simplicity) will be extracted			
	from the cohort according to the treatment chosen by the patient and a			
	description of each group will be performed.			
	accomption of each group will be performed.			
	Details of the statistical analyses, methods and data conventions will be			
	described in the SAP.			
	All statistical tests will be 2-sided and performed using a 0.05 significance level.			
	The selection of variables in multivariate analyses will be performed using a 0.2			
	significance level and a stepwise method. Whole the multivariate analyses			
	specified below involve the treatment and, in order to adjust for confounding,			
	all the potential confounding factors as explanatory variables.			
	The impact of the treatment chosen on the primary endpoint will be analysed			
	by means of a multivariate regression model with the AUC of the WURSS-K			
	during first 10 days of symptoms as dependent variable.			
	The impact of the treatment chosen on the cold symptoms' duration will be			
	analysed by means of a Cox model.			
	The impact of the treatment chosen on the risk to develop respiratory			
	complication requiring antibiotic prescription during a 20-day follow-up period			
	will be analyzed by a multivariate logistic model.			
	The impact of the treatment chosen on the intake of conventional common			
	cold medication (antibiotics, antipyretics, mucolytics, decongestants,			
	antitussives, systemic and topical corticosteroids) will be analyzed by			
	multivariate Poisson regressions for the numbers of days and a multivariate			
	logistic regression for the frequency.			
	logistic regression for the frequency.			

Version: 2.0; 08 Sep 2021 Page **18** of **61**

The impact of the treatment chosen on the number of family members in close contact developing common cold symptoms after the patient all over the study period will be analyzed by means of a multivariate Poisson regression.

- **Safety:** All adverse events and incidents will be listed, but only treatmentemergent adverse events/incidents (non-serious + serious)/ undesirable expected side effects will be summarized.

Two groups (called treatment groups) will be extracted from the cohort according to the treatment chosen by the patient.

Adverse events and incidents will be summarized by the number and percentage of patients (by treatment group), classified by System Organ Class and Preferred Term as defined by MedDRA dictionary.

For a given treatment group, a given adverse event will be counted treatment emergent only once per patient during the treatment period.

Frequency and percentage of patients with at least one reported adverse event/ incident/ expected side effect will be tabulated by System Organ Class and by treatment group.

Version: **2.0**; **08** Sep **2021** Page **19** of **61** Study Number: **LPH-2101**

3. Flow Chart

	ACUTE PHASE			FOLLOW-UP			
Visit name	Screening/Inclusion	At home	Telephone call	End of treatment	At home	Telephone call	End of study
Visit Number	V1		TC1	V2		TC2	V3
Days/Weeks	D1	D1 – D10	D5±2	D10±2	D11 – D30±5	D20±2	D30 ± 5
Screening and General Assessments							
Information and consent process	Х						
Eligibility criteria	Х						
Demography and Medical history	Х						
Physical and clinical examination	X			Х			Х
Ongoing medication	Х						
Patient's choice for using Healsea® Children self-administration or not	Х						
Treatment							
Acute phase (Healsea® Children or no saline irrigation as add on therapy)		Х					
Assessments							
Subject e-diary (WURSS-K)		Х			X*		
Adverse Events/incidents/undesirable expected side effects and concomitant medication reporting	Х	Х	Х	Х	х	х	Х

^{*} After D10, the WURSS-K will be assessed once daily until the subject feels not sick for two consecutive days if applicable.

Version: **2.0; 08 Sep 2021** Study Number: **LPH-2101**

4. Identification and description of the investigational Device

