8.1 General

8.1.1 Design type of clinical investigation

This is a prospective, open label, observational, national (Poland), multicentre study.

During this prospective observational study, one cohort of IgE-dependent allergic children with early symptoms of infectious rhinitis will be followed, children being treated with Healsea® Children on top of common cold conventional therapies or with conventional therapies only (nasal irrigation excepted). This observational study aimed to confirm the benefit of Healsea® Children in a real life setting in children with perennial allergy.

Page 29 of 61 Version: 2.0; 08 Sep 2021

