8.3 Subjects

The target population is allergic children with early symptoms of acute infectious rhinitis.

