8.3.1 Eligibility criteria

8.3.1.1 Inclusion criteria

Subjects will be enrolled if they meet all of the following criteria:

- 1. Male/Female subjects ≥6 and ≤10- year old
- 2. AsIgE ≥ class 2 (RAST) or positive prick test for at least one perennial allergen
- 3. Acute infectious rhinitis/rhinosinusitis for ≤48h before trial entry
- 4. Patient presenting with fever ≥ 37.5 °C at screening
- Symptoms of headache, muscle ache, chilliness, sore throat, blocked nose, runny nose, cough, sneezing with a total score ≤9 (according to a physician-rated symptom score; scale: 0 → 3 [0: no symptom to 3: severe intensity])
- 6. At least one of these symptoms: sore throat, runny nose or blocked nose (i.e., with a score ≥1)
- 7. Written consent obtained from parent/legal guardians
- 8. Written assent obtained from patient

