8.3.1.2 Non-inclusion Criteria

Subjects will not be enrolled if one of the following criteria is present:

- 1. Known hypersensitivity/allergy to any component of the test device
- 2. Medical history that is considered by the investigator as a reason for non-inclusion
- 3. Severe nasal septum deviation or other condition that could cause nasal obstruction such as the presence of nasal polyps
- 4. History of nasal or sinus surgery that in the opinion of the investigator may influence symptom scores
- 5. Antibiotic intake within 2 weeks before screening
- 6. Systemic corticosteroids within 4 weeks before screening
- 7. Antihistamines intake for allergy when treatment was started from less than 4 weeks
- 8. Bacterial lysate intake within 6 months before screening
- 9. Chronic decongestant use

Version: **2.0**; **08** Sep **2021** Page **32** of **61** Study Number: **LPH-2101**

- 10. Recent (within the previous 2 days) intake of a common cold medicine that in the opinion of the investigator may influence symptom score at screening (NSAID, nasal decongestants, cough medicines)
 - 8.3.2 Criteria and procedures for subject withdrawal or lost to follow-up

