8.3.8 Relationship of investigation population to target population

Healsea® Children will be used within its intended use. This observational study aimed to confirm the benefit of Healsea® Children in a real life setting in children with perennial allergy and early symptoms of infectious rhinitis.

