10.2. Analysis of the secondary efficacy criteria

The analysis of the secondary endpoints will involve multivariate analysis.

The selection of variables in multivariate analysis will be performed using a 0.20 significance level and a stepwise method. Whole the multivariate analyses specified below involve the treatment and, in order to adjust for confounding, all the potential confounding factors as explanatory variables:

- Temperature at baseline (°C);
- Symptoms' scores at baseline.

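### The target population is described in two ways, entry requires only sensitisation to a perennial allergen, and allergic rhinitis history is missing from the SAP's confounder list although families choose the treatment

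*Protocol*

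**What the plan says.** **Population.** The Target Population row of the protocol synopsis reads "Children with allergic rhinitis and symptoms of acute infectious rhinitis". Protocol 8.3 reads "The target population is allergic children with early symptoms of acute infectious rhinitis". Protocol 8.1.1 gives the aim as "This observational study aimed to confirm the benefit of Healsea® Children in a real life setting in children with perennial allergy", and 8.3.8 repeats it as the "benefit of Healsea® Children in a real life setting in children with perennial allergy and early symptoms of infectious rhinitis".

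**Entry.** The only inclusion criterion about allergy (Protocol 8.3.1.1, no. 2) is "AsIgE ≥ class 2 (RAST) or positive prick test for at least one perennial allergen". No criterion asks for a diagnosis, history or current symptoms of allergic rhinitis.

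**Outcome.** The WURSS-K total (Protocol 8.1.3) sums 14 items scored 0 to 3. Runny nose, stuffy nose and sneezing are three of them. Protocol section 5 describes allergic rhinitis by its typical nasal symptoms.

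**Comparison and analysis.** Patients or parents choose whether to use the spray (Protocol 8.2, 9.1). The primary test is an unadjusted t-test or Wilcoxon test (SAP 10.1), and only that result is treated as conclusive (SAP 6.3.1). SAP 10.2 says that the multivariate models take in every potential confounder. It then lists two, baseline temperature and "Symptoms' scores at baseline", and applies stepwise selection at 0.20.

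**The concern.** A positive test shows sensitisation. A sensitised child with no nasal allergy meets criterion 2, and so does a child with daily allergic rhinitis. Two consequences follow.

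First, a reader who takes the population from the synopsis would apply the result to children with allergic rhinitis, although the cohort was not selected for that.

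Second, allergic rhinitis is a plausible confounder here. It can produce symptoms that the outcome counts, and it can influence whether a family opts for a nasal spray. If it is unevenly spread between the self-chosen groups, part of the AUC difference reflects allergy and not treatment. Neither listed covariate can remove that part fully, because a baseline score for runny or blocked nose is the same number whichever cause produced it.

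**Working it through.** **1. The passages side by side.** Criterion 2 fits the wording of Protocol 8.1.1, 8.3 and 8.3.8. It does not fit the synopsis row, which requires more than the criterion tests. One further ambiguity is non-inclusion criterion 3, "Severe nasal septum deviation or other condition that could cause nasal obstruction such as the presence of nasal polyps". Protocol section 5 says that nasal allergy leads to obstruction, so a literal reading could exclude some of the children that the synopsis names.

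**2. The plan's own figure.** Protocol 7.4 and SAP section 4 state that 100 per group detect a standardised difference of 0.4 with 80% power at a two-sided 5% level. The normal approximation gives 99 per group and 80.7% power at 100. The exact t-test gives 99.1 and 80.4%. The figure reproduces, and this point does not disturb it.

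**3. What active allergic rhinitis could add to one child's AUC.** The documents give no value, so this is an illustration. Assume that it keeps runny nose, stuffy nose and sneezing at 1 point or more from D1 to D10. It then adds points only on days when the cold alone would have scored the item 0. The trapezoidal rule from D1 to D10 spans 9 one-day intervals.

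- Cold never scores these items (no overlap): 3 × 1 × 9 = 27 points. This is the ceiling.
- Cold keeps them at 1 or more through D7 and at 0 afterwards: the excess per item is 0.5 (D7–D8) + 1 (D8–D9) + 1 (D9–D10) = 2.5, so 3 × 2.5 = 7.5 points.
- Cold keeps them at 1 or more through D10: 0 points.

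Protocol 6.6 says that infectious rhinitis affects children for about 7 to 10 days, so the second and third cases are nearer to what the protocol expects.

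**4. Shift in the group contrast.** Assume that the prevalence of active allergic rhinitis differs by 15 percentage points between groups and that the AUC standard deviation is 30 to 50. Neither figure is in the documents. Shift in SD units = 0.15 × added points / SD. The last column takes the shift as acting against a true effect of 0.4 with 100 per group: power = Φ((0.4 − shift)/√(2/100) − 1.96).

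| Case | Added AUC | × 0.15 | Shift, SD 50 to 30 | Power |
|---|---|---|---|---|
| Cold through D10 | 0 | 0 | 0 | 80.7% |
| Cold through D7 | 7.5 | 1.125 | 0.02 to 0.04 | 76.1% to 72.7% |
| No overlap (ceiling) | 27 | 4.05 | 0.08 to 0.14 | 61.6% to 46.6% |

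**5. If allergic rhinitis is balanced.** There is then no bias, only extra variance. Assume a prevalence of 25% to 75% and an effect of 0.3 to 0.8 SD on AUC, added to a within-stratum SD of 1. Power is 74.7% to 80.1%.

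**The case against.** Four counter-arguments carry weight.

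- **The synopsis row is the exception.** The objectives, the hypothesis and Protocol 8.3 speak of allergic children, and the aim speaks of perennial allergy. A reader might infer that the trial sets out to conclude for children with allergic rhinitis. The documents do not support that: the rationale discusses allergic rhinitis, but no objective, hypothesis or SAP text frames the conclusion that way. This stands, and it reduces the population issue to an inconsistency that needs reconciling.
- **Indirect controls exist.** A reader might infer that allergic nasal disease is left wholly uncontrolled. That goes too far. Non-inclusion criteria cover "Antihistamines intake for allergy when treatment was started from less than 4 weeks", chronic decongestant use and other causes of nasal obstruction. Entry requires onset within 48 hours, fever and a limited symptom score. Baseline nasal symptoms are scored, compared between groups (SAP 8.4) and offered to the models. Medical history and earlier medication are tabulated by group (SAP 8.2, 8.3). The questionnaire asks the child about cold symptoms. For symptom duration, the recovery-date rule in SAP 10.2.2 limits the influence of lingering symptoms. None of these measures identifies allergic rhinitis in a model, however.
- **The 27 points are a ceiling.** A reader might take them as an estimate. They require that the cold itself never scores on three of its most typical symptoms, whereas every enrolled child must have acute infectious rhinitis.
- **The likely direction is conservative.** A reader might fear a spurious benefit. If families of children with troublesome allergic rhinitis prefer the spray, the shift raises AUC in the spray group and works against the device. The documents establish no direction, so this too is an assumption.

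What survives is that a plausible confounder in a non-randomised comparison is absent from a list described as complete, although medical history is already collected and coded.

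**Conclusion.** The point holds as an inconsistency in the stated population and an omission from the confounder list. The cohort is one of children sensitised to a perennial allergen, with an unknown proportion who have allergic rhinitis. Bias in the AUC contrast arises only if active allergic rhinitis differs between the self-chosen groups. Under the assumptions shown it runs from 0 to 0.14 SD, and is 0.02 to 0.04 SD if cold symptoms end after D7. These sizes rest on an assumed imbalance, an assumed SD and an assumed symptom pattern, so they indicate scale and do not predict a result. The documents show neither that an imbalance exists nor that the primary result would favour the device. The case for acting rests on how little the change costs more than on the size of the likely error.

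**What to change.** 1. **Reconcile the population wording.** Align the synopsis Target Population row with Protocol 8.3 and 8.3.1.1, and state the population and all conclusions as children sensitised to at least one perennial allergen. Leave the entry criterion unchanged. Requiring allergic rhinitis at entry would be a separate design trade-off, and it would turn the covariate below into a constant. Clarify in the same edit whether non-inclusion criterion 3 is meant to reach obstruction caused by allergy.
2. **Add the covariate.** Derive allergic rhinitis history (yes/no) from the medical history recorded at Visit 1 and MedDRA-coded under SAP 8.3. Show it by treatment group. Add it to the SAP 10.2 list as a fixed term, exempt from stepwise selection, in the AUC ANCOVA (SAP 10.2.1) and the symptom-duration Cox models (SAP 10.2.2).

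**Cost and limits.** The work is wording and programming, with one degree of freedom per model and no new data collection. History is an imperfect proxy for active disease and depends on how completely sites recorded it. The covariate does not correct the unadjusted primary test in SAP 10.1. That would require making the adjusted model the basis for the conclusion.
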